2.4.7.4 Outcomes

Delirium Diagnosis: Assessments will occur during preoperative testing (if applicable) and at the beginning of sessions 1-4. If the patient undergoes the session 4 MRI scan on a different day from the fourth EEG and DOT recording session, a CAM assessment will be completed prior to the patient entering the scanner. We will use the Confusion Assessment Method (CAM, long form)[67] to assign the presence or absence of delirium. The CAM is a validated tool for delirium diagnosis, with a sensitivity of 94% and specificity of 89%[68].

Administration of the CAM takes 10-20 minutes at our institution. If patients are also enrolled in The ENGAGES study (HRPO# 201407128), CAM assessment and CAM chart review data will be retrospectively and prospectively obtained from their research records to determine delirium diagnosis, severity, and duration, including both preoperative and postoperative assessments.

Delirium Severity: Delirium severity will be quantified using the CAM-S, a validated weighting of CAM subscores[69]. We will apply the long form of the CAM-S as it has a finer scale from 0 to 19.

Delirium Duration: # days of CAM+ will be determined by CAM outcome and from examination of the patient's electronic medical record through delirium chart review.

Pain level: Assessed using the Behavioral Pain Scale for the Non-Intubated Patient (BPS-NI) and the Visual Analog Scale (VAS) Pain Scores. If patients are also enrolled in The ENGAGES study (HRPO# 201407128), pain assessment data will be retrospectively and prospectively obtained from their research records, including both preoperative and postoperative assessments.

2.5.4 Aim 4: Investigate the relationship between preoperative DMN FC and postoperative delirium.

Hypothesis: Preoperative DMN FC measures will be greater for those who do not experience delirium and will vary inversely with peak postoperative delirium severity.

Analysis 1: A Mann-Whitney U-test will assess for differences in median DMN FC between those who did and did not experience delirium.

Expected Finding: Median preoperative DMN FC will be greater in those who do not experience delirium.

Analysis 2: Regression analysis will determine the correlation of peak delirium severity score and preoperative DMN FC.

Expected Finding: Preoperative DMN FC will vary inversely with peak delirium severity.

Interpretations and Future Directions: A lower median DMN FC for patients who developed delirium would reflect an underlying vulnerability against delirium and potentially pre-clinical Alzheimer's dementia. Subsequent studies could correlate plaque burden, DMN FC, and postoperative delirium risk. Further studies would also be needed to generate a reference range to address the possibility that high DMN FC is associated with protection against delirium. The strength of the correlation will be informative for whether fcMRI or fcDOT is more sensitive.

Problems/Alternative Approaches: **Recruitment.** We expect to enroll approximately 1 patient per week. Poor recruitment may require additional data acquisition into Year 2 or expansion of recruitment to patients scheduled for concomitant procedures or percutaneous aortic valve replacement. **Nuisance covariates.** Despite the smaller sample size, we will consider a MANOVA to account for age and years of education. We will incorporate postoperative day in the model if variance is high for postoperative intubation length. Magnitudes of beta value would then be assessed for relative contributions to predicting delirium. **Motion artifact.** If excessive during fcMRI or fcDOT acquisition, scanning length will be extended. We will also consider increasing head padding within the MR scanner coil. We will use frame censoring of motion artifact in our prior study[41]. **Sleep.** Fluctuations in arousal can potentially confound fcMRI during wakefulness[70]. We will record shorter (5-minute) epochs if patients are unable to remain awake for 10-minute scans.

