2.4.2 Pre-Study Period: None

2.4.3 Subject Screening, Enrollment, and Consent Process:

Sixty-six patients who have had cardiac surgery will be recruited in the Center for Preoperative Assessment and Planning (CPAP), Center for Advanced Medicine (CAM), cardiothoracic intensive care unit (CT-ICU), or step-down floors of Barnes-Jewish Hospital (BJH) in St. Louis. Depending on equipment and research personnel availability, patients may be recruited before or after surgery.

Given that the incidence of postoperative delirium is not predictable for an individual and to spare the cost and resources associated with consenting all cardiac patients, a partial HIPAA waiver will be obtained to allow preliminary eligibility screening of patients based on electronic medical records. Research personnel will screen the surgery schedule for Barnes-Jewish Hospital for procedures fitting the inclusion criteria the following week. Surgeries that meet inclusion criteria will then be screened for all eligibility criteria prior to surgery and being approached. Information regarding eligible patients will be kept in a screening log that will be destroyed once recruitment is complete.

Depending on equipment availability, research personnel may approach eligible patients in CPAP, CAM, CT-ICU, or step-down floors before surgery for consent. Patients consented before surgery will undergo preoperative fMRI, fcDOT, and EEG within one month before surgery, as well as a baseline CAM assessment. If patients are approached preoperatively and there is not enough time for preoperative testing to take place (i.e. patient enrolled day before surgery), patients will complete a baseline CAM assessment before surgery and participate in postoperative testing. Patients not consented before surgery will be approached as early as postoperative day 1 following surgery. To screen for dementia at baseline, we will apply the AD8[61].

Preoperative: For patients consented before surgery, full written informed consent will be obtained directly from the patient. Consent may take place in CPAP, CAM, CT-ICU or step-down floors of BJH. **The participant's previous medical record will be reviewed to ensure they meet all inclusion & exclusion criteria.**

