2.4.4 Inclusion/Exclusion Criteria

Table 1 lists the inclusion and exclusion criteria common to both patient study arms.

Inclusion Criteria	Exclusion Criteria
Age \geq 60	Implanted pacemaker
Surgery requiring cardiopulmonary bypass for Coronary artery bypass grafting (CABG), aortic repair/replacement, septal myectomy, and/or heart valve repair/replacement	Automatic internal cardiac defibrillator
English Speaking	Other implant for which MRI is contraindicated
	Concomitant cerebrovascular procedure or requirement of deep hypothermic circulatory arrest
	Inability to lay flat or still for MRI
	Legal blindness or severe deafness
	Seizure history
	Known focal brain lesion larger than 3 cm

Table 1: Common Inclusion and Exclusion Criteria for Study Enrollment

Delirium Case Arm: Delirious as diagnosed by the Confusion Assessment Method (CAM)/Confusion Assessment Method for the Intensive Care Unit (CAM-ICU) at some point during postoperative day 1-5. The presence of hypoactive delirium will be confirmed after consent has been obtained and prior to measurements.

Postoperative Control Arm: Not delirious as diagnosed by the CAM on postoperative day 1-5.

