2.4.5 Study Involvement

Preoperative Testing: Approximately 2 hours. This will occur within one month before surgery and will take approximately 2 hours total. A baseline CAM assessment will be completed at this time. Research personnel will also assess for pain using the Behavioral Pain Scale for Non-Intubated Patients (BPS-NI). Patients will then be asked to sit upright and still for 30 minutes while watching television or moving toes or fingers to maintain wakefulness. EEG and fcDOT data will be acquired. An additional 15 minutes of data will be acquired while patients keep their eyes closed. To maintain wakefulness, patients will be asked to keep moving toes or fingers. Patients will also listen to an auditory recording for 3 minutes while EEG and fcDOT data is acquired for source localization. Patients will then be asked to remain awake and still in an MRI scanner for 1 hour to allow fMRI data to be acquired. The MRI may not be performed on the same day as preoperative EEG and DOT due to the availability of the scanner. Pulse oximetry may be used during data acquisition, with supplemental oxygen, if needed.

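### Aim 4 relates peak postoperative CAM-S to preoperative DMN FC without using the baseline CAM, so symptoms present before surgery could be read as vulnerability to postoperative delirium

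*Combined protocol and SAP*

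**What the plan says.** Section 2.5.4 hypothesises that preoperative DMN FC is higher in patients who do not become delirious and "will vary inversely with peak postoperative delirium severity". Analysis 1 is a Mann-Whitney test of FC by delirium status. Analysis 2 reads "Regression analysis will determine the correlation of peak delirium severity score and preoperative DMN FC". Neither names a baseline severity term, a change score or a rule for patients with symptoms before surgery. The covariates mentioned are age and education (to be considered) and postoperative day (conditional). Section 2.5.5 leaves further covariates to future studies, and the preoperative CAM is not among them.

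The baseline assessment is planned in several places. Section 2.4.3: "Patients consented before surgery will undergo preoperative fMRI, fcDOT, and EEG within one month before surgery, as well as a baseline CAM assessment". Section 2.4.5, on the preoperative visit: "A baseline CAM assessment will be completed at this time". Section 2.4.7.4: "Assessments will occur during preoperative testing (if applicable) and at the beginning of sessions 1-4". Section 2.4.7.3 adds a CAM on the day of the preoperative MRI. On severity, Section 2.4.7.4 says: "We will apply the long form of the CAM-S as it has a finer scale from 0 to 19".

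Section 2.4.4 defines a case as delirious by CAM or CAM-ICU "at some point during postoperative day 1-5. The presence of hypoactive delirium will be confirmed after consent has been obtained and prior to measurements". It does not require a negative preoperative CAM.

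One sentence does link preoperative CAM data to severity. For patients also enrolled in ENGAGES, Section 2.4.7.4 obtains CAM records "to determine delirium diagnosis, severity, and duration, including both preoperative and postoperative assessments". It names a data source and gives no rule for using those data in an analysis.

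**The concern.** Aim 4 is the only aim built on FC measured before delirium, and Section 2.5.4 would read lower FC in patients who became delirious as a sign of vulnerability. The protocol's background supplies both links of an alternative explanation. Section 2.1.3 lists existing cognitive impairment as a delirium risk factor, and Section 2.1.5 says reduced DMN FC tracks the severity of Alzheimer's dementia. Section 2.4.3 screens for dementia with the AD8, but dementia is not an exclusion in Table 1 and the AD8 has no stated analytic use.

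A patient who is already inattentive or disorganised before surgery could therefore have both low preoperative FC and a raised CAM-S at every assessment. The planned slope would count those points as postoperative severity. In Analysis 1, a patient who was CAM-positive before surgery would contribute FC that does not come from a delirium-free state. The plan has no rule for that patient.

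**Working it through.** **Inputs.** The plan gives no power figure for this regression, so there is none to reproduce. The effect size of 0.8 in Section 2.6 belongs to the two-group FC comparison. The plan also gives no baseline CAM-S distribution, no correlation of baseline score with FC or with peak score, no number of patients with preoperative FC, and no alpha. Assumptions:
- n = 33 to 66. The target is 66 evaluable patients, and Section 2.4.3 allows recruitment after surgery, so the Aim 4 set may be smaller.
- Two-sided alpha 0.05.
- a = correlation of FC with baseline CAM-S, -0.2 to -0.4.
- b = correlation of baseline with peak CAM-S, 0.3 to 0.5.

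**Step 1: association carried by baseline alone.** If FC is related to the peak score only through baseline, the raw correlation is r = a × b:
- -0.2 × 0.3 = -0.06
- -0.3 × 0.5 = -0.15
- -0.4 × 0.5 = -0.20

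**Step 2: how often the planned regression is then significant.** By Fisher's z, with λ = atanh(|r|) × √(n - 3), the probability is Φ(λ - 1.96) + Φ(-λ - 1.96).

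For r = -0.15, atanh(0.15) = 0.151.
- n = 33: λ = 0.151 × √30 = 0.83, giving Φ(-1.13) + Φ(-2.79) = 0.13.
- n = 66: λ = 0.151 × √63 = 1.20, giving Φ(-0.76) + Φ(-3.16) = 0.22.

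| a | b | r | n = 33 | n = 66 |
|---|---|---|---|---|
| -0.2 | 0.3 | -0.06 | 6% | 8% |
| -0.3 | 0.5 | -0.15 | 13% | 22% |
| -0.4 | 0.5 | -0.20 | 20% | 36% |

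Simulation with normal scores (40,000 trials per case) gives 6% and 8%, 13% and 23%, and 20% and 37%. With baseline CAM-S in the model, the rate is 5% in every case.

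**Step 3: what adjustment does to precision.** Let r_YX be the correlation of FC with the peak score, assumed to be -0.35. Then R²_full = (r_YX² + b² - 2·r_YX·a·b) / (1 - a²). The ratio of adjusted to unadjusted standard error is √[(1 - R²_full) / ((1 - r_YX²)(1 - a²))].

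| a | b = 0.1 | b = 0.3 | b = 0.5 |
|---|---|---|---|
| 0 | 0.99 | 0.95 | 0.85 |
| -0.3 | 1.05 | 1.02 | 0.94 |
| -0.5 | 1.15 | 1.14 | 1.06 |

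For a = -0.3 and b = 0.5, R²_full = (0.1225 + 0.25 - 0.105) / 0.91 = 0.294, and the ratio is √[0.706 / (0.8775 × 0.91)] = 0.94. The standardised slope moves from -0.35 to (-0.35 + 0.15) / 0.91 = -0.22.

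**Step 4: comparison with a detectable effect.** The smallest correlation detectable with 80% power is tanh[(1.96 + 0.84) / √(n - 3)], which is 0.34 at n = 66 and 0.47 at n = 33. The largest baseline-only path above is 0.20.

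**The case against.** Four arguments carry weight.

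- **Baseline scores are probably low.** Patients with preoperative FC consent for themselves (Section 2.4.3), sit still for 30 minutes and lie in a scanner for an hour (Section 2.4.5). Few are likely to be CAM-positive beforehand. This stands as a limit on size. It does not rule out milder features, because no exclusion removes such patients and the baseline score is never reported.
- **Adjustment answers a different question.** Aim 4 asks about a relationship, and the marginal slope is a legitimate answer to that. If low FC and subtle preoperative inattention share a cause, adjustment removes part of what the aim studies. This stands. It is a reason to report both slopes and to let neither decide alone.
- **The AD8 may be the better adjuster.** The mechanism concerns cognitive impairment, whereas the CAM captures acute, fluctuating symptoms and may be done up to a month before surgery. That is fair, but baseline CAM-S is the same scale as the outcome and shows directly how many points were present beforehand.
- **Preoperative CAM-S scoring is an inference.** The plan never says the preoperative CAM will be scored for severity. It follows only from the long-form CAM being the stated instrument.

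A reader might also infer that omitting baseline costs precision. The documents do not support that. The standard error falls clearly when baseline is unrelated to FC and well correlated with the peak score, but the confounding needs baseline to be related to FC, and in those cases the standard error may rise or fall.

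**Conclusion.** The point holds as an inexpensive improvement to Aim 4. The plan schedules a baseline CAM for the patients Aim 4 analyses, gives no rule for using it, and does not require cases to be CAM-negative before surgery. An inverse slope could therefore partly reflect symptoms that preceded the operation.

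The size cannot be fixed from the documents. Under the assumed correlations, the baseline-only path makes the planned regression significant in about 6% to 37% of trials. The low end is close to the nominal 5%, and the effect is negligible if nearly all baseline scores are 0.

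A reader might go further and infer that an inverse slope could not be told apart from preoperative symptoms at all. That is not supported. The assumed paths give a correlation of at most 0.20, short of the 0.34 detectable with 80% power at n = 66, so they could not alone produce an association that large. Nor are the extra significant results false under the plan's marginal question. They mislead only if read as vulnerability beyond symptoms already present.

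**What to change.** In Section 2.5.4:

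1. **Analysis 2.** Keep the planned unadjusted slope. Report beside it the slope adjusted for baseline CAM-S, scored from the preoperative long-form CAM, and show the baseline CAM-S distribution.
2. **Analysis 1.** Repeat the Mann-Whitney test without any patient who was CAM-positive before surgery.
3. **Interpretation.** Discuss vulnerability in light of both slopes, and state that adjustment may remove part of a shared cause.

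The cost is a few lines of analysis text, the scoring of an assessment already planned, and one degree of freedom. No visit or procedure is added. If baseline scores sit at the floor, little is gained beyond documenting that the concern is empty.

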2.5.5 Sub-studies

EEG and fcDOT from patient controls will be used for case-control studies or for improving the technology of fcDOT. Some evidence suggests that blinks and eye movements may be useful for the detection of delirium[71]. Once larger samples sizes are obtained, age, years of education, surgical and anesthetic exposure,

cardiopulmonary bypass duration, and aortic cross clamp time will be used in future studies as nuisance covariates.

2.6 Sample Size

Sample Size Justification: The study has been powered to compare differences in DMN FC between patients who did and did not experience delirium. While universal agreement in sample size is lacking, FC studies employing 15 minutes of scanner time and 15 or more individuals produce reliable fcMRI maps[72]. We anticipate the ability to observe large effects (effect size 0.8, beta 0.2, power 0.8) based on conventions for statistical power analysis in the behavioral sciences.[73]

2.7 Management of Intercurrent Events

2.7.1 Cross-over

There will be no planned cross-over of participants in this study. Patients who develop delirium over the course of the study will be assigned to the delirium arm.

2.7.2 Adverse Experiences

The investigator will closely monitor subjects for evidence of adverse events in this minimal risk study. All adverse events will be reported to the IRB and followed until satisfactory resolution. The description of the adverse experience will include the time of onset, duration, intensity, etiology, relationship to the study, and any treatment required.

2.7.3 Premature Discontinuation

Patients will be withdrawn if discontinuation is in the best interest of the patient or if the patient requests withdrawal from the study for any reason.

2.7.4 Potential Risks

Interruption of clinical care: Timing of studies could potentially interfere with nursing, therapy, or medical assessments.

Discomfort related to EEG: Skin abrasions from scalp electrode placement or discomfort on removal of electrodes.

Discomfort related to DOT: No adverse effects have been reported with diffuse optical tomography, although it is possible that effects not yet reported may occur. The LED light used to make the measurements has very low power (less than 4 mW/mm² at 800 nm) and below the ANSI limit for long-term exposure to infrared light. As the power is substantially less than that used in pulse oximetry, a standard anesthetic monitoring device uses the similar technology, even the risk of burns is very remote. The procedure does not cause stress or discomfort. Though unlikely to occur, the imaging cap may press or scrape uncomfortably against the scalp, producing a light skin reaction.

Non-contrast MRI: Claustrophobia, anxiety, discomfort from headphones used to shield out noise, hearing loss due to hammering noise. Additionally, patients with tattoos could experience irritation, swelling, heating, or instances of primary or secondary burns in the area of the tattoo. Patients with devices such as a pacemaker, bone hardware, or a device placed in their uterus may experience heating or movement of the device, device malfunction, or damage to the tissue that surrounds the device. These risks are unlikely to be common or severe. There have been no adverse events noted for 3T MRI studies of patients with coronary stents, sternal wires, cardiac valves, or even retained temporary pacemaker wires[74].

Breach of Confidentiality: Another potential risk of participating in this study is that confidential information about the participant may be accidentally disclosed. We will use our best efforts to keep the information about participants secure, through de-identification of personal health information. We think the risk of accidental disclosure is very small.

2.8 Procedures to Minimize Potential Risks

Interruption of clinical care: The research team will be in open discussion with patients and nursing staff to ensure that there is no disruption in the patient's clinical care, comfort, and recovery. Depending on logistical constraints, preoperative testing and session 4 may be split up to maximize convenience for our patient and alignment with MRI scanner availability. For example, DOT and EEG for session 4 may be acquired while the patient remains in the hospital whereas fMRI may be performed as an outpatient due to scheduling conflicts. A study physician will be present during the scanning of inpatients to address the risks associated with an MRI scan in a remote location. Additionally, if the participant is still in the hospital, the scan will be scheduled to occur after chest tubes have been removed and the patient is close to hospital discharge.

EEG: Timing and manner of electrodes and adhesive removal will be based on patient's comfort and convenience. Discomfort will be minimized based on the use of sticker/adhesive/gel electrodes and not needle electrodes.

DOT: Placement and removal of cap adjustment will be undertaken to minimize any discomfort for the patient.

MRI Safety: The patient will be thoroughly screened for MRI-incompatible implants. Scans may be performed prior to surgery (Preoperative testing) and/or postoperatively, after removal of any temporal pacemaker wires and removal of chest tubes. Cardiac stents and valves will be checked to confirm compatibility. The MRI scan will occur at least 3 days after surgery to ensure that granulation tissue has formed around any sternal wires and minimize any risk of dislodgement. Scans performed on inpatients or after recent discharge (Session 4) will occur within the hospital (5th floor MIR or CCIR on 10th floor of BJH). A study physician will be present for inpatient scans.

Confidentiality: This will be maintained by assigning each participant a number to be linked with data. Any protected health information of patient participants will be stored in a locked drawer within the locked office of the PI. Electronic protected health information will be stored on a password-protected server.

Research Conduct: Studies are conducted at Washington University School of Medicine under the general supervision of a board-certified cardiac anesthesiologist who is familiar with postoperative surgical care. Patients will be monitored during the study session by trained research personnel.

Participant Satisfaction: Physical and psychological risks to subjects will be minimized by obtaining feedback from participants. Patients studied during delirious episodes will be approached for full informed consent following recovery from their altered mental status if delirium resolution occurs before hospital discharge.

Data and Safety Monitoring Plan

The investigator will closely monitor subjects for evidence of adverse events. All adverse events will be reported to the IRB and followed until satisfactory resolution.

